11.4 Final Analysis Plan

Primary outcome analyses (intention to treat):

Asymptomatic Cohort Primary Analysis:

Those with asymptomatic exposure: Incidence of COVID 19 disease by day 14 will be assessed via Fisher's Exact Test.

Symptomatic Cohort Primary Analysis:

Those with symptomatic disease at study entry: For a summary metric of the change in symptom severity over 14 days, a longitudinal change over time repeated measures mixed-regression model will estimate the treatment effect by study arm. Subjects without symptoms are coded as a zero severity. Persons hospitalized or dead are coded as 10 severity.

Participants who become symptomatic with COVID19 on Day 1 before receiving the study medicine will be described with the symptomatic cohort.

Secondary Analyses:

For the asymptomatic with exposure cohort, the primary analysis (intention to treat) will be repeated for participants who received at least one dose of the study medicine.

- Secondary endpoints will be assessed via Fisher's Exact test and median (with interquartile ranges) as appropriate.
- Those with symptomatic disease at study entry: Proportional odds models will be used to assess the ordinal scale for disease severity at day 14 (illness without hospitalization, hospitalization without ICU stay or death, or hospitalization with ICU stay or death).
- Severity of overall symptoms at Day 0, 1, 5, and 14 is recorded on a 0-10 visual analog scale. Severity of symptoms at Day 5 will be compared first as a categorical analysis (no symptoms vs. symptoms) via Fisher's Exact Chi Square.
 - Second among those with symptoms, the 0-10 visual analog scale severity data will be compared via independent two-sample *t* test. If data are non-normally distributed, then data will be compared via Mann-Whitney U by study arm.

A priori subgroup analyses will include assessment by:

- Confirmed SARS-CoV-2 disease or disease exposure
- Healthcare worker vs. Household contact
- Days from Exposure
- Decile of age
- Sex as a biological variable
- Censored subjects, who became symptomatic before receipt of the first dose of study medicine on D#1, will be separately analyzed and reported.

Handling of withdrawn subjects.

If there is a large lost to follow up / study discontinuation rate, then the primary endpoint for the asymptomatic cohort would have a secondary analysis to assess incidence as a 3-category analysis of: i) no disease, ii) incident disease, or iii) unknown.

Similarly, the symptomatic cohort would add a fourth category of unknown.

Participants who stop taking the study medicine but who agree to be followed for 14 days will be assessed as intent-to-treat. On Day 14, we will ask for other medications or vitamins that were taken during the study period.

Screened Persons

Persons who are screened but not enrolled will be summarized in CONSORT diagrams and other descriptive summaries of their COVID-19 related information – with all data de-identified.

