3.2 Study Outcome Measures

3.2.1 Primary Outcome Measures

Asymptomatic Cohort

- Incidence of COVID-19 disease within 14 days (among those asymptomatic at baseline)

Symptomatic Cohort

- Change in symptom severity score (visual analog scale 0-10) over 14 days

[figure not shown]

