7.2 Enrollment/Baseline

Randomization (Day 0)

- Participants will be randomized by a computer-generated algorithm using a permuted block randomization sequence.
- Randomization will be stratified by symptomatic vs. asymptomatic status at baseline.
- Investigational pharmacy will dispense the masked study medicine
- Study personnel will then FedEx study medicine to the participant
- Participant will be sent an email to expect medication to arrive by 10:30am

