7.3 Follow-up

Day 1 Virtual visit

- Verify receipt of study medicine
- Clinical status check-in
 - Participant starts study medicine (4 tabs), then 3 tabs in 6-8 hours, then 3 tabs daily.
- Query for SARS-CoV-2 testing
- Query for symptom status (0-10 visual analog scale of symptom severity)
- Query for hospitalization or SAEs
- Query for medication-related side effects / AEs

Day 3 Virtual visit

- Query for symptom status (0-10 visual analog scale of symptom severity)
- Query for hospitalization or SAEs
- Query for medication-related side effects / AEs

Day 5 Virtual visit

- Query for symptom status (0-10 visual analog scale of symptom severity)
- Assessment of adherence by self-report
- Completion of study medicine, which has a ~7 day half-life
- Query for study medicine side effects since enrollment
- Query for SARS-CoV-2 testing
- Query for hospitalization or SAEs

Day 10 Virtual visit

- Query for symptom status (0-10 visual analog scale of symptom severity)
- Query for SARS-CoV-2 testing

- Query for SARS-CoV-2 testing
- Query for hospitalization or SAEs

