7.4 Final Study Visit

- Day 14 Visit
 - Query for symptom status (0-10 visual analog scale of severity)
 - Query for study medicine side effects since enrollment
 - Query for SARS-CoV-2 testing
 - Query for hospitalization or SAEs
 - Query for pregnancy status
 - Final outcome assessment
 - Assess other medicines used during study period
 - Optional dried blood spot collection, return in pre-paid envelope.

If participations have a SAE prior to the final study visit (e.g. hospitalization), the final resolution of the event will be followed until resolution or up to 90 days. The hospitalization eCRF will be sent in 14 days interval to assess clinical outcome / resolution of the hospitalization. Pregnancies will be followed through delivery to assess for any teratogenic SAE.

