- d. The primary outcome will be presented by subgroups formed by COVID test results (confirmed positive vs. other), age groups (18-35, 36-50, > 50), sex, and days from exposure onset to entry. These are apriori subgroups defined in the Version 1.0 of the protocol.
- e. Medication adherence is captured on study day 5. Another subgroup of interest is comparing the treatment groups for change in symptom severity score after day 5 by adherence reported at day 5 ($\leq 75\%$ versus $> 75\%$).

II. Secondary outcomes

- a. Secondary outcomes for incidence will be presented as proportions and compared between the treatment groups with Fisher’s Exact tests.
- b. Symptom severity scores were recorded with the online participant surveys at days 3, 5, 10 and 14 only for those who responded “yes” to “Any symptoms experienced”.

- i. Visual analog scale (0-10) for “overall symptom severity” is collected via a digital slider bar, which is marked with “0 = no symptoms”; 5 (placed in the middle); and “10 = severe symptoms”

Severity of overall symptoms?

Please click to move the slider, even if your symptoms are a 5

* must provide value

0 = No symptoms 5 10 = Most severe

- ii. For those who responded “no” to “Any symptoms experienced” the symptom severity score for that visit is assigned as zero.
- iii. For those hospitalized or with deaths, their symptom severity was scored as 10 if they did not respond to the visit survey.
- iv. Analysis is by Kruskal Wallis tests among those with symptoms at day 14.

Clarifications (24 May 2020):

- Participants with missing outcome data are still included in the denominator, as the trial is performed as an intent to treat analysis.
- Sensitivity analyses were performed excluding participants with missing data from the denominator as well as including participants with missing data as events.

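### The symptom-score days conflict across the documents, and no pre-dose baseline is secured for the symptomatic cohort's primary outcome

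*Combined protocol and SAP*

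**What the plan says.** Protocol section 3.2.1 defines the symptomatic cohort's primary outcome as "Change in symptom severity score (visual analog scale 0-10) over 14 days". Section 11.4 analyses it by a model described only in general terms: "a longitudinal change over time repeated measures mixed-regression model will estimate the treatment effect by study arm". That paragraph gives the coding for people without symptoms, in hospital or dead. It does not say which visits enter, which score is the baseline, or whether baseline is a covariate.

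The days on which the score is taken appear in three places:

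- Protocol 11.4, in a bullet under the secondary analyses: "Severity of overall symptoms at Day 0, 1, 5, and 14 is recorded on a 0-10 visual analog scale".
- Protocol 7.3, at each of the virtual visits on days 1, 3, 5 and 10, in an item that begins "Query for symptom status (0-10 visual analog scale of symptom severity". Section 7.4 adds day 14, beginning "Query for symptom status (0-10 visual analog scale of severity".
- SAP II.b, under the heading "II. Secondary outcomes": "Symptom severity scores were recorded with the online participant surveys at days 3, 5, 10 and 14 only for those who responded" yes to having symptoms. Those who answered no are assigned zero.

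The enrolment section, 7.2, under the entry beginning "Randomization (Day 0", lists the randomization method, the stratification, dispensing, shipping and an email to the participant. It lists no severity score.

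**The concern.** A change outcome is only as well defined as its starting point. Here the one list that contains a clearly pre-dose day is not matched by the procedures for that day. The SAP, written in the past tense about what was recorded, contains neither Day 0 nor Day 1.

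Two things are at stake. First, if the earliest usable score comes after dosing has begun, any early drug effect is already in it, and a change or slope measured from that score understates the effect or can turn its sign. Second, without a pre-dose score the model cannot adjust for how ill people were at entry. Leaving the baseline unnamed also allows it to be chosen after the data have been seen.

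**Working it through.** There is no stated figure to reproduce. The check sets the lists side by side and then asks whether each early day can serve as a baseline.

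| Source | Day 0 | Day 1 | Day 3 | Day 5 | Day 10 | Day 14 |
|---|---|---|---|---|---|---|
| Protocol 11.4 | yes | yes | no | yes | no | yes |
| Protocol 7.3-7.4 | no | yes | yes | yes | yes | yes |
| SAP II.b | no | no | yes | yes | yes | yes |
| Lists naming the day | 1 of 3 | 2 of 3 | 2 of 3 | 3 of 3 | 2 of 3 | 3 of 3 |

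The consent section (14.3) gives the follow-up surveys as days 1, 3, 5, 10 and 14, which agrees with 7.3-7.4.

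**Day 0.** This is the day of randomization. Medicine is then shipped and started on Day 1, so a Day 0 score would be pre-dose. Section 11.4 says it is recorded. Section 7.2 does not list it, section 7.1 (screening) lists only eligibility and consent, and section 15.3 places symptom reports in the follow-up period. No procedure in the available text collects it.

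**Day 1.** Section 7.3 puts the start of study medicine and the severity query in the same visit, with the medicine listed first, and asks about drug side effects that day. The participant timeline in section 7 places the first four tablets before the Day 1 survey. No rule fixes the order, so a Day 1 score may fall on either side of the first dose.

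**Day 3 onward.** These scores come after dosing has started and cannot be baselines.

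**The model.** The primary-analysis paragraph of 11.4 does not resolve the matter, because it names no days.

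An illustration, with assumed mean scores and not trial data, shows why the choice matters. Take placebo at 6, 5 and 1, and drug at 6, 4 and 1, on days 0, 3 and 14.

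- Change from Day 0 to Day 14: placebo 1 - 6 = -5; drug 1 - 6 = -5. The difference is 0.
- Change from Day 3 to Day 14: placebo 1 - 5 = -4; drug 1 - 4 = -3. The drug arm appears to improve by 1 point less, although it was better on Day 3 and equal on Day 14.

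The illustration shows the mechanism only. A Day 1 score given a few hours after the first dose would plausibly carry much less drug effect than a Day 3 score. Because arms are randomized, a comparison of score levels at a later visit is not biased by the missing baseline. The distortion affects change and slope, and change is how this outcome is defined.

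**The case against.** The strongest reply is that 11.4 does state a Day 0 score, and Day 0 precedes the first dose. That stands. A reader might infer from the SAP list that the symptomatic primary outcome has no baseline at all, or that change is measured from Day 3. The documents do not support either reading. The SAP list sits under secondary outcomes, the SAP's only primary-outcome heading is for the prophylaxis study, and no text makes Day 3 a baseline. SAP items I.d-e read like treatment-cohort text, so the SAP's scope is unclear, but that is not enough to say how the symptomatic primary would be computed.

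A reader might also infer that 11.4 drops days 3 and 10 from the primary model. It does not. Its day list belongs to a secondary-analysis bullet leading into the Day 5 comparison, and the sentence on the primary model is separate.

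The silence of 7.2 is also limited evidence. That section is mainly about randomization and shipping, and no schedule table is visible under Appendix A in the text available, so a Day 0 item may exist there. If it does, part of the fix becomes wording only. Sections 7.2-7.4, 11.4 and SAP II.b would still disagree, and the model would still name no baseline.

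Finally, the textbook variance reduction of one minus the squared correlation applies to adding a baseline covariate to an unadjusted comparison at a single time. It does not carry over to a repeated-measures model with several visits, so it cannot size the loss here.

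**Conclusion.** The point holds in this form: the three day lists conflict, and the plan does not secure or name a pre-dose baseline for a primary outcome defined as change. It goes beyond missing detail, because following the visit schedule as written may yield no score known to precede treatment.

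No numerical size is claimed. The gain from adjustment depends on the correlation between baseline and later scores, which the documents do not give, and on the covariance structure of the model. The bias from a post-dose baseline depends on how early any effect appears. Whether either loss occurs depends on whether a Day 0 score is in fact collected, which the available text leaves open. The correction is cheap and should be made before the symptomatic primary is analysed.

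**What to change.** 1. In section 7.2, list the existing 0-10 slider as an item on the Day 0 enrolment form. If it is already collected, this is a change of wording only.
2. In section 11.4, name that pre-dose score as the baseline, include it as a covariate in the mixed model, and name days 3, 5, 10 and 14 as the outcome visits.
3. For participants with no Day 0 score, use the Day 1 score as baseline only where it is documented to precede the first dose. Otherwise treat baseline as missing. Using Day 1 for everyone would mix pre-dose and post-dose values. The available text describes no record of survey time against dose time, so this route may cover few people.
4. Make sections 7.2-7.4, section 11.4 and SAP II.b give the same days, and say in the SAP which cohort and outcome its list serves.

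The cost is one item on an existing web form plus protocol and SAP wording. No visit is added.

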Primary Endpoint in Asymptomatic Cohort	
 ● Incidence of COVID-19 disease within 14 days among those who are asymptomatic with known exposure
Primary Endpoint in Symptomatic Cohort	
 ● Change in symptom severity score (visual analog scale 0-10) over 14 days
Secondary Endpoints	
 1. Incidence of Hospitalization for COVID-19 or death 2. Incidence of confirmed SARS-CoV-2 detection 3. Incidence of possible COVID-19 symptoms 4. Incidence of all-cause study medicine discontinuation 5. Severity of symptoms at Day 5 and 14 by visual analog scale 6. Ordinal Scale of COVID-19 disease maximum severity at day 14 among those who are symptomatic at trial entry
Duration of Participation	
Recruitment and follow up will be internet-based.
 
 ● 14 days of active participation ● Up to 90 days follow up for those with COVID-19 diagnosis to assess final outcome or dried blood spot collection for antibody serologies.
Inclusion Criteria	
 ● Exposure to COVID-19 within 4 days, either as: 
 ○ Occupational exposure, or ○ Household contact. 
OR
 
 ● Individual with symptomatic COVID-19 disease confirmed by PCR+ or by compatible symptoms with exposure to known PCR+ case with <=4 days of symptoms. ● Age >=18 years of age ● Provision of Informed Consent
Exclusion Criteria	
 ● Current hospitalization ● Allergy to chloroquine or hydroxychloroquine ● Prior retinal eye disease ● Concurrent malignancy requiring chemotherapy ● Known Chronic Kidney disease, Stage 4 or 5 or dialysis.

	
 • Known glucose-6 phosphate dehydrogenase (G6PD) deficiency. • Known Porphyria • Weight <50 kg • Structural or ischemic heart disease • Personal or family history of QT prolongation • Current use of: hydroxychloroquine, chloroquine, mefloquine, or cardiac medicines of: amiodarone, digoxin, dofetilide, flecainide, procainamide, propafenone, or sotalol • Current use of QT prolonging medicines, including azithromycin (Refer to protocol for full list).

Stratification
	
Randomization will be stratified by baseline status of COVID-19 disease vs. asymptomatic with exposure. Analyses will be separate for asymptomatic vs. symptomatic cohorts

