11.2 Sample Size Considerations

Two cohorts of 1500 subjects each:

- 1) Asymptomatic persons exposed to COVID-19 disease (750 in placebo, 750 in intervention);
- 2) Symptomatic outpatient COVID-19 disease (750 in placebo, 750 in intervention).

Assuming 90% power, a two-sided alpha = 0.05 and loss to follow-up up to 20%, for each cohort the planned sample size is 750 participants per arm based on the following assumptions:

- 10% transmission rate from COVID-19 cases to close contacts
- For those with symptomatic illness the proportions at day 14 in the placebo group are 90%, 8% and 2%, respectively for illness without hospitalization, hospitalization with ICU stay or death, and hospitalization with an ICU stay or death.

The estimated transmission rates are uncertain. Table 1 below (for the asymptomatic cohort with exposure) shows that we are well powered to detect even a smaller (40%) relative reduction in the incidence of COVID 19 with 80% power for transmission rates of at least 10% with placebo. Table 2 (for the symptomatic group) shows that we are well powered to detect a common odds ratio of 0.6-0.75 under the assumption that the control proportions for illness without hospitalization, hospitalization without ICU stay or death and hospitalization with ICU stay or death are 90%, 8% and 2%, respectively.

Table 1. Sample Size Table for Asymptomatic Participants (Healthcare worker or household contact) With Exposure

Estimated transmission rate with placebo	Estimated transmission rate with drug	Percent relative reduction in transmission rate	Sample size (per arm) with 90% power	Sample size (per arm) with 80% power
10%	5%	50%	621	474
	6%	40%	1014	771
12%	6%	50%	509	389
	7.2%	40%	831	632
15%	7.5%	50%	398	304
	9%	40%	648	493

Table 2. Sample size table for participants with symptomatic disease, assuming that the control proportions are 90% illness with no hospitalization, 8% hospitalization with no ICU stay or death and 2% hospitalization with ICU stay or death.

Log Odds Ratio	Odds Ratio	Sample size (per group) with 90% power	Sample size (per group) with 80% power
0.60	1.82	805	601
0.65	1.91	697	521
0.70	2.01	610	456
0.75	2.12	539	403

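### Section 11.4 splits the Day 5 symptom score into a yes/no test and a comparison among those still symptomatic, without saying which one answers the severity question

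*Combined protocol and SAP*

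**What the plan says.** The protocol Summary lists as a secondary endpoint "Severity of symptoms at Day 5 and 14 by visual analog scale". For Day 5, Section 11.4 (Secondary Analyses) plans two comparisons in sequence:

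- Step 1: "Severity of symptoms at Day 5 will be compared first as a categorical analysis (no symptoms vs. symptoms"), by Fisher's test.
- Step 2: "Second among those with symptoms, the 0-10 visual analog scale severity data will be compared via independent two-sample" *t* test, or Mann-Whitney if the scores are not normally distributed.

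The bullet names no cohort and gives no rule for combining the steps or choosing between them.

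Participants without symptoms already have a value on the scale. Section 11.4 says "Subjects without symptoms are coded as a zero severity", and the SAP (Secondary outcomes, II.b.ii) says that for anyone reporting no symptoms "the symptom severity score for that visit is assigned as zero". The symptomatic cohort's primary analysis uses those zeros: "a longitudinal change over time repeated measures mixed-regression model will estimate the treatment effect by study arm". The SAP's own severity test is for Day 14, again only among those with symptoms; it does not say how Day 5 is tested.

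**The concern.** The endpoint is severity, yet no test specific to Day 5 uses the severity score in everyone randomised. In step 1 a participant who falls from 8 to 1 counts the same as one who stays at 8. This matters most in the symptomatic cohort, where everyone enters ill and many may still have some symptoms at Day 5.

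Step 2 does use the score, but only in people who are not yet symptom-free. Those groups are no longer the randomised groups. If the drug clears mild illness, the active arm's remaining participants are the sicker ones.

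At stake is how one early secondary result is read. Two tests can disagree, even in direction, and the plan leaves it open which one would be reported as the Day 5 finding.

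**Working it through.** **The plan's own figures.** No power is stated for Day 5. The nearest figures are in Table 2 of Section 11.2, for the three-level Day 14 scale. The proportional-odds formula per group is n = 6(z₁ + z₂)² / [θ²(1 − Σp̄ᵢ³)], where θ is the log odds ratio, z₁ and z₂ are the normal quantiles for alpha and power, and p̄ᵢ is the average of the two arms' category proportions. With θ = 0.60 and control proportions 90/8/2%, the active arm is about 94.3/4.6/1.1% and Σp̄ᵢ³ is about 0.782. Then n = 6 × 10.51 / (0.36 × 0.218) ≈ 804 at 90% power and 6 × 7.85 / (0.36 × 0.218) ≈ 601 at 80%, against 805 and 601 in the table. The other rows also agree within one. The table reproduces, but it concerns another scale and another day.

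**Inputs for Day 5.**
- From Section 11.2: 750 per arm, up to 20% loss, two-sided 5%. Evaluable: 750 × 0.80 = 600 per arm.
- Assumed, because the documents give nothing: 10% to 50% of placebo symptom-free; remaining scores 1 + beta-binomial(9; 2, 3), with mean 1 + 9 × 2/5 = 4.6; and a common odds ratio for a worse score at every cut. An odds ratio of 0.75 is a mean difference of about 0.4 points.

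**False positives.** Two nearly independent 5% tests give 1 − 0.95² = 9.75%. Simulation under no effect gave 8.7% to 9.7% for at least one significant step, and 4.6% to 5.9% for one rank test on all scores.

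**Power at odds ratio 0.75** (%, simulated, 1,500 trials per setting in the main runs):

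| Placebo symptom-free | Step 1 alone | Either step at 5% | Either step at 2.5% | Full-scale rank test |
|---|---|---|---|---|
| 10% | 33 | 74 | 64 | 82 |
| 20% | 50 | 76 | 64 | 82 |
| 30% | 64 | 76 | 64 | 81 |
| 50% | 68 | 73 | 61 | 76 |

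The columns come from separate runs. Simulation error is about one point (√(0.8 × 0.2 / 1,500) = 0.010). A further run gave 73–77% for either step at 5%, 62–65% at 2.5% each, and 75–82% for the full-scale test.

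**Other effects.**
- Odds ratio 0.70: either step at 5% gave 88–91%, against 89–94% for the full-scale test. With 2.5% for each step the loss was 9 to 12 points.
- Odds ratio 0.60: the two-step plan and the full-scale test differ by about 1 point.
- Resolution only (symptom-free 10% to 15%, 20% to 27% or 30% to 37%): Fisher 71–80%, full-scale 34–56%.
- Severity among the symptomatic only (a separate set of runs, 10% or 30% symptom-free): Fisher about 4%; full-scale 74% or 38%; either step at 2.5% 79% or 69%.
- About 90% symptom-free, as in the prophylaxis cohort: the full-scale test gains only about 3 points over step 1 (28% against 25%).

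**Direction of step 2.** Take 30% of placebo symptom-free and a drug that only clears scores 1 to 3, making a further 8% of the cohort symptom-free. Under the assumed distribution, scores 1, 2 and 3 have shares 0.077, 0.126 and 0.151 of the symptomatic, so their mean is (0.077 + 0.252 + 0.453) / 0.354 = 2.21.
- Whole-cohort mean, placebo: 0.70 × 4.6 = 3.22. Active: 3.22 − 0.08 × 2.21 = 3.04, which is better by 0.18.
- Mean among those with symptoms, placebo: 4.6. Active: 3.04 / 0.62 = 4.91, which is worse by about 0.3.

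In simulations of such a drug, step 2 was significant in about 41–50% of trials, with the helped arm looking worse. In one such setting the yes/no test had 89% power and the full-scale test 22%.

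**The case against.** The strongest reply is that the plan is a two-part analysis and must be judged as a whole. A reader might take the first table row (82% against 33%) to mean that the plan gives up 49 points of power. The documents do not support that. Step 2 is also planned, and the two steps together at 5% each come within a few points of the full-scale test. Nor can one count both tests for the false-positive rate and only the first for power. The fair comparison holds the two steps to 5% in total, and there the loss shrinks as the effect grows.

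Three further points stand. First, no single test is best for every effect. For resolution only, the yes/no test is stronger, and for severity only, the two steps do better than the full-scale test even at 2.5% each. Second, the primary mixed model already uses the full 0–10 score, and Day 5 is one of its visits (Section 7.3), so it would be wrong to infer that a general reduction in severity goes untested. Third, the plan claims no multiplicity control for any secondary endpoint, so the 9–10% is not a breach of a stated error rate.

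None of this tells the reader which Day 5 test is the answer, or makes step 2 a randomised comparison.

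**Conclusion.** The point holds as one of definition and validity more than of lost power. The Day 5 severity question has two tests and no designated answer. One ignores severity above zero, and the other conditions on a post-randomisation state and can reverse the apparent direction of benefit.

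With total error held to 5%, the split costs about 14 to 20 points at an assumed odds ratio of 0.75. That figure rests on conditions that the documents neither state nor exclude: a modest effect, spread over the whole scale. A reader might instead carry over the odds ratio of 1.82 in Table 2 and conclude that there is no loss. At that size even step 1 alone loses 7 points or less with 10% or more symptom-free, but that effect was set for the Day 14 hospitalisation scale and says nothing about Day 5 symptoms.

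The consequence is limited: one timepoint of a secondary endpoint in the symptomatic cohort, with the primary analysis unaffected.

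**What to change.** In Section 11.4 and the SAP, for the symptomatic cohort:

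- Name one Day 5 test of the full 0–10 score in all randomised participants: a rank-sum test, or a proportional odds model with a common odds ratio and 95% CI. Section 11.4 already plans that model for the Day 14 ordinal scale.
- Keep 0 for no symptoms, and state one rule for scoring hospitalised or dead participants as 10. Section 11.4 applies the 10 without condition, while SAP II.b.iii applies it only when the visit survey was not answered. The two must be reconciled.
- Report the symptom-free percentage by arm, with the difference and 95% CI, as supportive. Report scores among those with symptoms as descriptive only.

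If the sponsor expects mainly an effect on resolution, it should say so beforehand and pre-specify one combined two-part test at 5% instead.

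The cost is a sentence or two and no new data. The price is lower power if the effect is confined to resolution, or to severity among those who stay symptomatic, and an effect measure that is less direct to read than a percentage.
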